4.3.2. CAT Score Responders

4.3.2.1. Definition of Endpoint

The COPD Assessment Test (CAT) is an 8-item questionnaire used to measure the health status of patients with COPD, participants rate their experience on a 6-point scale, ranging from 0 (no impairment) to 5 (maximum impairment) with a scoring range of 0-40. Higher scores indicate greater disease impact.

The variable of interest is the proportion of CAT score responders at Week 52. A participant is considered a responder if they have a 2-point or more improvement (reduction) in CAT Score from baseline. Participants who withdrew from study prior to Week 52 will be included in the analysis as a non-responder.

Participants who experienced an intercurrent event of IP discontinuation or interruption of 2 or more consecutive doses of IP associated with the COVID-19 pandemic will be considered as having missing data from the time of the event. For these participants missing data will be imputed using a MAR assumption based on the observed on- and off-treatment scores recorded by randomized participants (prior to occurrence of any intercurrent events of IP discontinuation or interruption of 2 or more consecutive doses of IP associated with the COVID-19 pandemic), the response status of these participants will be determined based on the imputed value.

Imputed data will be combined with the observed data and analyzed multiple times using logistic regression analysis. The results of these analyses will be combined using Rubin's rule.

The summary measure of treatment effect will be the odds ratio which represents the relative odds of a participant being a responder at Week 52 in the mepolizumab arm compared with placebo.

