7.2. Participant Discontinuation/Withdrawal from the Study

A participant may prematurely discontinue study intervention product and withdraw from the study at any time at his/her own request, or at any time at the discretion of the investigator for safety, behavioural, compliance or administrative reasons.

Participants may withdraw from the PK sub-study and remain in the study.

Participants who permanently discontinue IP are not required to withdraw from the study. If a participant must permanently discontinue IP, every effort should be made by the Investigator/site staff to keep the participant in the study to collect important efficacy and safety data. Participants who have permanently discontinued IP and have not withdrawn consent may continue in the study to complete all remaining protocol specified visits by continued in-clinic visits (or home healthcare, if applicable) or by phone contact.

For participants who discontinue IP but remain in the study, an IP discontinuation Visit should be conducted as shown in SoA. See SoA (Section 1.3) for data to be collected at the time of IP discontinuation. If for any reason those participants later withdraw from the study, a withdrawal from the study Visit should be conducted as shown in the SoA. Additional details will be given in the SRM.

For participants who discontinue IP and withdraw from the study at the same time, the Withdrawal from study Visit should be conducted as per SoA.

If the participant withdraws consent for disclosure of future information, the sponsor may retain and continue to use any data collected before such a withdrawal of consent.

If a participant withdraws from the study, he/she may request destruction of any samples taken and not tested, and the investigator must document this in the site study records.

Any participant who withdraws from the study prior to their planned Completion of Study date (defined in Section 4.4) will be considered to have missing data from the date of study withdrawal up to their planned Completion of Study date.

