Secondary	
For all secondary endpoints the target population, treatment comparison and strategies for intercurrent events will be the same as for the primary estimand.
 
For the evaluation of the time to the first moderate/severe exacerbation, the summary comparison between treatments will be the hazard ratio.
 
Analysis of this variable will use a Cox's proportional hazards model allowing for covariates of smoking status (current vs previous smoker), number of exacerbations in previous year, baseline disease severity (as % predicted post-bronchodilator FEV₁) and geographic region. Missing values will be considered as censored at random (non-informative censoring). Summaries and graphs of the Kaplan-Meier estimates of the proportion of participants with a moderate/severe exacerbation over time will be produced.
 
The proportion of CAT score responders at Week 52 will be evaluated, and participants with missing values at Week 52 not associated with disruptions or restrictions imposed due to the COVID-19 pandemic on or before the Week 52 visit, will be included in the analysis as a non-responder. Sensitivity analyses to the assumption regarding missing data will be performed using multiple imputation methods based on pattern mixture models. Analysis will be performed using a logistic regression model adjusting for baseline CAT score, smoking status and geographic region.
 
The proportion of SGRQ Total score responders at Week 52 will be evaluated, and participants with missing values at Week 52 not associated with disruptions

Endpoint	Statistical Analysis Methods

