All assessments from Visit 5 and onwards stated in the SoA tables in Section 1.3.1 and 1.3.2 can be performed through home healthcare with the exception of the Exit Visit, and the below procedures, which must be performed in clinic:

- Pre-bronchodilator spirometry;
- Clinician rated response to therapy; and
- Physical examinations

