4.2.2. Main analytical approach

Statistical Methodology Specification

Endpoint / Variables					
Annualized rate of moderate or severe exacerbations (mITT, mITT2 and Per Protocol).					
Model Specification					

Data from previous studies show the numbers of moderate/severe exacerbations follow a negative binomial distribution. The primary analysis of the annualized rate of moderate/severe exacerbations will use a negative binomial model, including both on-treatment and, where available, off-treatment exacerbation data.
 
The analysis model will include covariates as shown below and an offset variable of \log_e (length of time in study) which reflects the period of time in the study for which exacerbation data has been recorded for inclusion in the analysis model. Missing data will be considered as missing at random (MAR).
 
 
 Fixed Categorical:	Treatment group, Geographic Region, Smoking Status	
 
 Fixed Continuous:	Baseline disease severity (as % predicted post-bronchodilator FEV₁), number of moderate/severe exacerbations in previous year ($\leq 2, 3, \geq 4$ as ordinal)	
 
 
 Participants with missing covariate information will be excluded from the analysis. 		Fixed Categorical:	Treatment group, Geographic Region, Smoking Status	Fixed Continuous:	Baseline disease severity (as % predicted post-bronchodilator FEV ₁), number of moderate/severe exacerbations in previous year ($\leq 2, 3, \geq 4$ as ordinal)
Fixed Categorical:	Treatment group, Geographic Region, Smoking Status				
Fixed Continuous:	Baseline disease severity (as % predicted post-bronchodilator FEV ₁), number of moderate/severe exacerbations in previous year ($\leq 2, 3, \geq 4$ as ordinal)				
Model Checking & Diagnostics					

 Missing data is assumed missing at random. Departures from this assumption will be tested for the primary endpoint (see Section 4.2.3). Models will be checked for issues with convergence. 					
Model Results Presentation					

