4.3.2.2. Main Analytical Approach

Descriptive statistics by visit will be presented for the mITT population up to Week 104, regardless of treatment discontinuation. Responders will be summarized by visit up to Week 52 for the mITT and mITT2 populations, and by visit up to Week 104 for the Extended Treatment population.

Statistical Methodology Specification

Model Specification

- | |
|---|
| 
 • A logistic regression model will be used to compare the proportion of responders in the mepolizumab arm compared to placebo for the mITT and mITT2 populations. • The analysis model will include the following terms: |
|---|

Fixed Categorical:	Treatment group, smoking status, geographic region
Fixed Continuous:	Baseline score

 Participants with missing covariate information will be excluded from the analysis 	
Model Checking & Diagnostics	

 Models will be checked for issues with convergence. 	
Model Results Presentation	

 The number and percentage of participants identified as responders, non-responders and the number with missing data imputed due to experiencing a COVID-19 pandemic related intercurrent event of IP discontinuation or interruption of 2 or more consecutive doses of IP prior to Week 52 will be displayed by treatment group, the non-responder group will be further categorized to display the number of participants withdrawn early from the study before Week 52 and the number with missing visit data. The estimated odds ratio, 95% CI and p-value comparing treatments from the logistic regression models will be displayed. A forest plot of the estimated odds ratio and 95% CI for the comparison of treatment groups will be provided by visit. 	
Subgroup Analyses	
Separate exploratory subgroup analyses will be carried out as outlined in Section 4.10.1 .	

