4.3.4. E-RS: COPD total score Responders

4.3.4.1. Definition of Endpoint

The Evaluating Respiratory Symptoms in COPD (E-RS: COPD) consists of 11 items from the 14 item EXACT instrument (completed each evening using an eDiary). E-RS: COPD is intended to capture information related to the respiratory symptoms of COPD, i.e., breathlessness, cough, sputum production, chest congestion, and chest tightness. The E-RS: COPD has a scoring range of 0-40, higher scores indicate more severe symptoms. Three subscales of the E-RS: COPD are used to describe different symptoms (breathlessness, cough and sputum, and chest symptoms).

Daily data will be slotted to baseline and 4-week periods relative to the first dose of IP as defined in Section 6.2.5.4.

The variable of interest is the proportion of E-RS: COPD responders at Week 52, using data from the 4-week period prior to Week 52 (Weeks 49-52). A participant is considered a responder if they have a 2-point or more improvement (reduction) in their average E-RS: COPD total score during a 4-week period compared to baseline (*E-RS™: COPD User Manual, 2016*). Participants who withdrew from study prior to the start of the Weeks 49-52 time-period will be included in the analysis as a non-responder.

Participants who experienced an intercurrent event of IP discontinuation or interruption of 2 or more consecutive doses of IP associated with the COVID-19 pandemic prior to Weeks 49-52 will be considered as having missing data from the time of the intercurrent event. Missing data will be imputed based on the average 4-weekly scores as described in Section 4.3.2.1.

The summary measure of treatment effect will be the odds ratio which represents the relative odds of a participant being a responder at Weeks 49-52 in the mepolizumab arm compared with placebo.

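### The SAP narrows the protocol's COVID-19 exception for the Week 52 responder endpoints and drops their pattern-mixture sensitivity analyses, and lists neither change

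*SAP*

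**What the plan says.** **Protocol 9.4.1.** For each of the CAT, SGRQ and E-RS: COPD responder endpoints, the participants counted as non-responders are those described as "participants with missing values at Week 52 not associated with disruptions or restrictions imposed due to the COVID-19 pandemic on or before the Week 52". The test is the cause of the missing value. For each of the three endpoints the protocol adds: "Sensitivity analyses to the assumption regarding missing data will be performed using multiple imputation methods based on pattern mixture models".

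**SAP 4.3.2.1 (CAT) and 4.3.3.1 (SGRQ).** "Participants who withdrew from study prior to Week 52 will be included in the analysis as a non-responder". **SAP 4.3.4.1 (E-RS: COPD).** "Participants who withdrew from study prior to the start of the Weeks 49-52 time-period will be included in the analysis as a non-responder". None of these sentences has a COVID-19 exception. Imputation under missing at random (MAR) applies only after a COVID-associated dosing event: stopping study product, or missing at least two doses in a row.

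**SAP 4.3.2.2.** The results display subdivides the non-responder group into those "withdrawn early from the study before Week 52 and the number with missing visit data".

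**SAP 4.2.2.** On the MAR assumption: "Departures from this assumption will be tested for the primary endpoint". The details follow in SAP 4.2.3 and concern the annualized exacerbation rate.

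**SAP 4.12, Table 1.** It lists five changes from Protocol Amendment 6: the mITT2 population, exacerbations by treatment type, prohibited-medication handling, early release of PK data, and the PK similarity criterion.

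**The concern.** The two documents sort some participants differently. The protocol asks why the Week 52 value is missing; the SAP asks whether a COVID-related dosing event occurred. A value lost to COVID-19 restrictions without such an event is exempt from non-response in the protocol but not in the SAP. Separately, the protocol's robustness check on the responder results has disappeared.

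These endpoints are steps 3, 4 and 5 of the fixed testing sequence, and step 6 (exacerbations needing an ED visit or hospitalization) is tested only if they succeed. An unlisted change in how participants are classified therefore bears on formal inference, and the three odds ratios would be reported without the promised test of their missing-data assumption.

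**Working it through.** **1. Which participants are classified differently?**

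- *Case (a), all three endpoints.* A participant stops study product for a non-COVID reason and stays in the study, which is permitted ("Participants who permanently discontinue IP are not required to withdraw from the study", Protocol 7.2). COVID-19 restrictions then lead to study withdrawal. The protocol exempts the missing value from non-response; the SAP scores a non-responder, because the dosing event was not COVID-related.
- *Case (b), CAT and SGRQ only.* A fully dosed 52-week participant never has the Exit Visit because of COVID-19 restrictions. Protocol 10.10.2.1 says assessments "can be performed through home healthcare with the exception of the Exit Visit", and no dose is due at that visit, so no dosing event can arise from missing it. The SAP definition gives no rule for this participant. The display in SAP 4.3.2.2 places missing visit data inside the non-responder group, so this case is an inference from the table layout.
- *Not affected by case (b).* E-RS: COPD (diary completed at home); a late visit, which is still analysed (SAP 6.2.5.1); and extended-treatment participants, whose Week 52 visit may be done at home (Protocol 1.3.2).
- *Overlap.* A participant who stops study product for a COVID-19 reason and also leaves the study meets both the non-responder sentence and the MAR sentence. No order of precedence is stated. SAP 4.3.1.1 does settle the same overlap for time to first exacerbation, by censoring at the earlier date.

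**2. Are the sensitivity analyses elsewhere in the SAP?** SAP 4.2.3 covers the primary endpoint. SAP 4.3 carries over the population, treatment condition and intercurrent-event handling from 4.2.1, but not the analyses in 4.2.3. The imputation in 4.3.2.1 is part of the main analysis under MAR, so it does not test that assumption. The term pattern mixture does not appear in the SAP.

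**3. Is either change recorded?** None of the five Table 1 entries covers them. The prohibited-medication entry concerns an intercurrent event, not missing Week 52 values.

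**4. Size.** The documents give no responder rates, no share of values missing in this way, and no planning figure for these endpoints, so there is nothing to reproduce. The primary-endpoint sample size is unaffected. What follows is an illustration on assumed inputs.

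Assume a placebo response of p0 = 0.45 and a true odds ratio of 1.50. The mepolizumab odds are 1.50 × 0.45/0.55 = 1.227, so p1 = 1.227/2.227 = 0.551. If a share m of an arm is scored as non-response and those participants would otherwise have responded at the arm's rate, then p′ = p(1 − m). The odds ratio is [p1′/(1 − p1′)] / [p0′/(1 − p0′)]. With 400 per arm, shares of 2%, 5% and 8% are 8, 20 and 32 participants.

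| m, mepolizumab / placebo | p1′ | p0′ | Odds ratio |
|---|---|---|---|
| 2% / 2% | 0.540 | 0.441 | 1.49 |
| 5% / 5% | 0.5235 | 0.4275 | 1.47 |
| 8% / 8% | 0.507 | 0.414 | 1.46 |
| 5% / 3% | 0.5235 | 0.4365 | 1.42 |
| 3% / 5% | 0.5345 | 0.4275 | 1.54 |

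With no true effect (both arms at 0.45), equal shares leave the odds ratio at 1.00; 5% / 3% gives 0.96 and 3% / 5% gives 1.04. Changing the placebo response to 40% or 50% moves the values by about 0.01 at most: 5% / 5% gives 1.476 or 1.465, and 5% / 3% gives 1.427 or 1.408.

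**The case against.** The omission of the sensitivity analyses has no good rebuttal: the protocol states them outright, and leaving detail to the analysis plan does not license dropping them. The objections concern the COVID-19 exception.

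- *The protocol names no method for COVID-missing responders and leaves the detail of the hypothetical strategy to the analysis plan.* True, so MAR imputation is not strictly a restoration of protocol text. It is, however, the SAP's own method for COVID-missing data, and the protocol is explicit that such values are not covered by its non-response rule.
- *The affected cases are few.* Probably. Participants off study product are offered telephone follow-up, and data from an unscheduled visit can be re-assigned to Week 52 (SAP 6.2.5.3). This limits the size of the discrepancy but does not remove it.
- *Precedence can be read from the layout, because COVID-imputed participants are shown separately from non-responders.* This is a reasonable reading, but it is not stated.
- *Blinding makes unequal shares unlikely, and equal shares barely move the odds ratio.* This stands as an argument for a small expected effect. Balance is still an assumption, and non-response scoring is not reliably conservative: the 3% / 5% row exceeds 1.50.
- *Other outputs address missingness.* The change-from-baseline repeated-measures models (SAP 4.4.4), the counts of missing visits by arm (4.3.2.2) and the compliance summaries (6.5.2) give context. None varies the missing-data assumption behind the responder odds ratio.

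**Conclusion.** Both parts hold. The SAP replaces a cause-based COVID-19 exception with a narrower one based on dosing events, and omits sensitivity analyses that the protocol commits to for each of three confirmatory secondary endpoints. Table 1 lists neither change. The omission is plain from the text. The narrowing is plain for study withdrawals (case (a)) and inferred from a table layout for missed Exit Visits (case (b)).

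The effect of the narrowing is unknown from the documents. On the assumed inputs it is a slight dilution if the arms are balanced (1.50 to between 1.49 and 1.46) and a shift in either direction if they are not (1.42 or 1.54). The missing sensitivity analyses matter whatever the COVID-19 counts turn out to be. The plan should be corrected, though the primary analysis is untouched.

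**What to change.** - In SAP 4.3.2.1, 4.3.3.1 and 4.3.4.1, extend the MAR imputation to every Week 52 value (Weeks 49-52 for E-RS: COPD) that is missing because of COVID-19 disruption, including COVID-related study withdrawals. State that this takes precedence over non-response.
- State in those definitions that all other missing values are non-response, instead of leaving it to the table layout.
- Add the protocol's pattern-mixture multiple-imputation sensitivity analysis for each of the three responder endpoints.
- If any departure is intended, list it with a reason in Table 1. The precedence rule is needed in either case.

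The cost is SAP wording and a few extra imputation runs. The COVID-19 reason is already available: Protocol 10.10.2 has missed visits recorded as COVID-19 deviations, and SAP 6.1.6 already summarises disposition by relationship to the pandemic.

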4.3.2.2. Main Analytical Approach

Descriptive statistics by visit will be presented for the mITT population up to Week 104, regardless of treatment discontinuation. Responders will be summarized by visit up to Week 52 for the mITT and mITT2 populations, and by visit up to Week 104 for the Extended Treatment population.

Statistical Methodology Specification

Model Specification

- | |
|---|
| 
 • A logistic regression model will be used to compare the proportion of responders in the mepolizumab arm compared to placebo for the mITT and mITT2 populations. • The analysis model will include the following terms: |
|---|

Fixed Categorical:	Treatment group, smoking status, geographic region
Fixed Continuous:	Baseline score

 Participants with missing covariate information will be excluded from the analysis 	
Model Checking & Diagnostics	

 Models will be checked for issues with convergence. 	
Model Results Presentation	

 The number and percentage of participants identified as responders, non-responders and the number with missing data imputed due to experiencing a COVID-19 pandemic related intercurrent event of IP discontinuation or interruption of 2 or more consecutive doses of IP prior to Week 52 will be displayed by treatment group, the non-responder group will be further categorized to display the number of participants withdrawn early from the study before Week 52 and the number with missing visit data. The estimated odds ratio, 95% CI and p-value comparing treatments from the logistic regression models will be displayed. A forest plot of the estimated odds ratio and 95% CI for the comparison of treatment groups will be provided by visit. 	
Subgroup Analyses	
Separate exploratory subgroup analyses will be carried out as outlined in Section 4.10.1 .	

4.3.3. SGRQ total score Responders

4.3.3.1. Definition of Endpoint

The St George’s Respiratory Questionnaire for COPD (SGRQ-C) is a 40-item questionnaire. A Total score and three component scores, a Symptoms score, Activity score and Impacts score will be calculated based on the scoring algorithm detailed in the SGRQ-C Manual Version 1.3. The total score is expressed as a percentage of overall impairment with 100 representing the worst possible health status and 0 the best possible health status. Higher scores indicate greater impairment of health.

The variable of interest is the proportion of SGRQ total score responders at Week 52. A participant is considered a responder if they have a 4-point or more improvement (reduction) in SGRQ total score from baseline. Participants who withdrew from study prior to Week 52 will be included in the analysis as a non-responder.

Participants who experienced an intercurrent event of IP discontinuation or interruption of 2 or more consecutive doses of IP associated with the COVID-19 pandemic will be considered as having missing data from the time of the event. Missing data will be imputed as described in Section [4.3.2.1](#).

The summary measure of treatment effect will be the odds ratio which represents the relative odds of a participant being a responder at Week 52 in the mepolizumab arm compared with placebo.

4.3.3.2. Main Analytical Approach

Descriptive statistics and summaries of responders for the SGRQ total score will be presented as detailed in Section 4.3.2.2. SGRQ total score responders will be analyzed as described in Section 4.3.2.2. Separate exploratory subgroup analyses will be carried out as outlined in Section 4.10.1.

